7.4.6 Suspected Unexpected Serious Adverse Reaction (SUSAR)

A SUSAR is a serious adverse reaction whose nature and severity exceed what is outlined in the Investigator's Brochure, the approved product label, or summary of product characteristics for marketed drugs.

During vaccine clinical trials, the sponsor is required to promptly report any confirmed or suspected SUSARs related to the study vaccine to the research team, ethics committee, Center for Drug Evaluation (CDE), and national health authorities. Upon receiving a SUSAR report from the sponsor, the investigator should immediately submit it to the ethics committee. If the sponsor and investigator disagree on causality with the vaccine but either party considers a connection possible, the sponsor must still expedite the report.

For SUSARs that are life-threatening or fatal, the sponsor must report as soon as possible within seven days of first awareness, with follow-up information provided within the subsequent eight days (note: the day the sponsor first becomes aware is day

0). For SUSARs that are non-fatal and non-life-threatening, the report must be made as soon as possible within 15 days of awareness. The sponsor should also promptly report any other potential serious safety risks to the national drug evaluation authorities, providing medical and scientific assessments for each case. The sponsor must continue to follow up on SAEs, submitting additional information or updates to the previous report within 15 days of receiving new data.

In the event of a SUSAR, the sponsor, investigator, ethics committee, or regulatory authorities have the authority to propose pausing or terminating the study.

7.4.7 Adverse Events of Special Interest (AESIs)

AESIs, specifically suspected cases of herpes zoster, will be collected from the first dose through 30 days after completing the full immunization.

7.4.8 Disease-Related Events Not Meeting AE or SAE Criteria

- 1) Elective surgeries planned before subject enrollment are not reported as SAEs.
- 2) Pregnancy itself is not considered an AE.

7.4.9 Development Safety Update Report (DSUR)

The sponsor must submit the Development Safety Update Report (DSUR) to the National Medical Products Administration's Center for Drug Evaluation (CDE), all investigators and clinical study sites, and the ethics committee in accordance with regulatory and ethics committee requirements. The DSUR should include relevant information on SAEs occurring within six months after full immunization and an assessment of the study risks and benefits.

7.5 Pregnancy and Postpartum Information

7.5.1 Subjects Who Become Pregnant During the Study

Pregnancy is an exclusion criterion for each vaccine dose, and women of childbearing potential are required to use effective contraception for eight months following the first vaccine dose. However, accidental pregnancies may still occur during participation. Any pregnancy occurring from the time of vaccination through six months after full immunization must be reported, and the investigator is required to complete a "Pregnancy Event Report Form."

Researchers will closely follow pregnant subjects to obtain pregnancy outcome information (e.g., details of delivery and newborn status, or termination of pregnancy) and update the "Pregnancy Event Report Form."

Pregnancy itself is not considered an AE, but any complications during pregnancy are considered AEs and, in certain cases, may be classified as SAEs, such as spontaneous

abortion, stillbirth, or congenital anomalies in the infant. Elective abortions due to personal choice, where no fetal abnormalities are present, are not considered adverse events.

Handling Pregnancy Events During Vaccination:

If pregnancy occurs after the first dose but before the completion of the full vaccination course, the subject should not receive the second dose until the pregnancy ends (whether full-term, miscarriage, or abortion). The investigator will maintain regular contact with the subject for pregnancy assessments.

If pregnancy is discovered after the subject has completed the full vaccination course, the subject may complete study visits per the protocol and investigator discretion.

7.6 Immunogenicity Evaluation

Evaluable subjects (those meeting all inclusion criteria, adhering to protocol-defined procedures and intervals, and without any exclusion criteria) will have their immunogenicity assessed using data obtained from ELISA and flow cytometry. The immunogenicity metrics include seroconversion rate, anti-gE antibody GMC, geometric fold increase, and the proportion of VZV gE-specific CD4+/CD8+ T cells expressing at least two cytokines (TNF- α , IFN- γ , IL-2, CD40L), comparing post-vaccination results to baseline.

7.6.1 Biological Sample Collection

Blood sample collection: Section 3.1.1.1. Suspected herpes zoster case sample collection: Section 3.1.1.2. Urine sample collection: Section 3.1.1.3

7.6.2 Biological Sample Processing

Serum Antibody Testing Sample:

Collect 4.0-5.0 mL of venous blood. Separate the serum within 24 hours and divide it into three tubes: one for testing and two as backups. The test sample should contain at least 0.5 mL and be stored below -20°C. Serum samples must remain frozen during transport, with dry ice used if necessary.

Cellular Immunity Testing Sample:

- 1) Collect 15.0-20.0 mL of venous blood into an anticoagulant tube (EDTA.K2, sodium heparin, or lithium heparin), gently inverting to mix with the anticoagulant. Keep the tube upright at room temperature, labeled correctly.
- 2) To avoid hemolysis, control the flow to allow blood to flow gently along the tube wall.
- 3) Within 3 hours of collection, mix fresh anticoagulated blood with saline (1:1 ratio),

carefully layer over lymphocyte separation medium (double the volume of anticoagulated blood), and centrifuge at 400g for 20 minutes. Collect the second layer of cells. Follow the “Human Peripheral Blood Lymphocyte Separation Medium Manual” for detailed instructions.

- 4) Add 4 mL of cell cryopreservation solution to the separated lymphocytes, aliquot into four cryovials (minimum 0.8 mL per tube), gradually cool, and store in liquid nitrogen.
- 5) Transport frozen samples with liquid nitrogen.
- 6) Backup samples should be stored at a third-party laboratory designated by the sponsor.

Herpes Zoster Suspected Case Biological Sample:

Place the swab or crust sample into a tube with viral preservation solution, store at -70°C or lower within 4 hours, and transport on dry ice to the testing laboratory.

7.6.3 Biological Sample Numbering Rules

Each biological sample should correspond to the subject study ID. Specific numbering guidelines should follow the relevant SOP.

7.6.4 Biological sample testing

Immunogenicity Biological Samples

A third-party testing agency will be commissioned to use the ELISA method to detect the anti-gE antibody levels in all serum samples from subjects.

A third-party testing agency or XXX central laboratory will be commissioned to use flow cytometry to analyze gE-specific CD4+/CD8+ T cell activation cytokines and the proportion of cells active for at least two cytokines (TNF- α , IFN- γ , IL-2, CD40L). Detailed procedures for cellular immunity indicators can be found in the operation manual or SOP of the third-party testing agency or the XXX central laboratory.

8. Statistical Considerations

8.1 Statistical Hypotheses

This study hypothesizes that, 30 days after full immunization with the study vaccine, the proportion of gE-specific CD4+/CD8+ T cell activation with at least two cytokines (TNF- α , IFN- γ , IL-2, CD40L) is non-inferior to that of the active control vaccine. The statistical hypotheses are as follows:

H10: On day 30 post-full immunization, the difference in the proportion of specific CD4+ T cell activation with at least two cytokines (TNF- α , IFN- γ , IL-2, CD40L)

between the experimental vaccine group and the active control vaccine group is $\leq -10\%$.
H11: On day 30 post-full immunization, the difference in the proportion of specific CD4+ T cell activation with at least two cytokines (TNF- α , IFN- γ , IL-2, CD40L) between the experimental vaccine group and the active control vaccine group is $> -10\%$.
H20: On day 30 post-full immunization, the difference in the proportion of specific CD8+ T cell activation with at least two cytokines (TNF- α , IFN- γ , IL-2, CD40L) between the experimental vaccine group and the active control vaccine group is $\leq -10\%$.
H21: On day 30 post-full immunization, the difference in the proportion of specific CD8+ T cell activation with at least two cytokines (TNF- α , IFN- γ , IL-2, CD40L) between the experimental vaccine group and the active control vaccine group is $> -10\%$.

8.2 Sample Size Determination

Assuming that, 30 days after full immunization, the proportion of gE-specific CD4+ T cell activation with two or more cytokines (IFN- γ , TNF- α , IL-2, CD40L) is 85% in the experimental vaccine group and 75% in the active control group, and the proportion of gE-specific CD8+ T cell activation with two or more cytokines is 55% in the experimental vaccine group and 45% in the active control group, with an assumed dropout rate of 10%, a sample size of 150 subjects per group will yield 135 evaluable subjects per group. At a one-sided significance level of 0.025, this sample size provides approximately 90% power to test the above non-inferiority hypothesis.

8.3 Analysis Sets

Full Analysis Set (FAS): This includes all subjects in both the experimental vaccine group and the similar active control vaccine group who follow the intention-to-treat (ITT) principle. Subjects must have been randomized, completed vaccination, and have baseline and at least one post-immunization immunogenicity result. For subjects with vaccination number errors, immunogenicity evaluation will follow the original randomized group.

Per-Protocol Set (PPS): This set includes all subjects in the experimental and active control vaccine groups who meet inclusion/exclusion criteria, are randomized, complete vaccination, and have baseline and 30-day post-full immunization immunogenicity results. Subjects with major protocol deviations impacting immunogenicity evaluation will be excluded, though data prior to deviations may still be included in the analysis.

Safety Set (SS): This includes all subjects who received any dose of the vaccine.

Safety analyses for each dose will be based on the actual number of subjects who received each dose. Specifically: The first-dose safety set includes all randomized subjects who received the first dose of the study vaccine. The second-dose safety set includes all randomized subjects who completed the second dose of the study vaccine.

Safety analyses for each dose will follow the ASAT (All Subjects As Treated) principle, analyzing subjects based on the vaccine group they actually received.

The determination of the above analysis sets will occur in a blinded data review meeting before database lock, with input from the primary investigator, sponsor, statisticians, and data managers.

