5.1.8 Medical Observation

After each dose of the study vaccine, the subject must be observed on-site for 30 minutes. The investigator will provide the subject with a Diary Card, thermometer, pen, and ruler, and guide them on how to measure and record their body temperature (axillary temperature) for 7 days after vaccination (the day of vaccination and the following 7 days), as well as record all adverse events. The subjects will be trained on how to use the thermometer and ruler, and how to monitor for adverse events and complete the Diary Card. A time will be scheduled for the collection of the Diary Card on day 7 after vaccination, along with the distribution of the Contact Card, and instructions on how to record all adverse events occurring between days 7-30 after vaccination. The Contact Card will be collected and reviewed 30 days after each dose of the vaccine.

The investigator will emphasize the researcher phone number on the Informed Consent Form and Diary Card, and instruct the subjects to immediately contact the investigator if they experience any symptoms or signs they consider severe or if they experience an event requiring hospitalization.

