5.1.9 Safety Follow-up

5.1.9.1 Follow-up Time

- (1) After each vaccine dose, the subject will be observed on-site for 30 minutes to monitor for any immediate adverse events.
- (2) After each vaccine dose, subjects will be given a Diary Card containing information on potential adverse events. Subjects are instructed to measure their temperature daily and record all local and systemic adverse events from the day of vaccination to day 7, as per the instructions on the Diary Card.
- (3) On day 7 after each vaccine dose, subjects will return the Diary Card, and the researcher will review and document any adverse reactions. Additionally, a Contact Card will be issued to the subjects to record adverse events from day 7 to day 30 after each dose.
- (4) From the first vaccine dose to 6 months post-completion of the full immunization

schedule, adverse events (SAEs) and pregnancy-related events will be collected through active reporting by the subject and periodic telephone follow-up by the researcher.

(5) During each visit, the researcher will remind subjects that they can contact the researcher at any time through the phone numbers listed on the Diary Card, Contact Card, or Informed Consent Form.

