7.3.3 Safety Assessment

The safety analysis cohort will include all subjects who meet the following criteria:

- Have received at least one dose of the study vaccine or control vaccine according to randomization;
- Have sufficient data for safety analysis (at least one dose and follow-up for safety);
- Have not received other prohibited medications or vaccines per protocol. For detailed information on the safety follow-up time and content, please refer to Section 5.1.9.

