8.4.4 Safety

This study will primarily focus on the statistical analysis of treatment-emergent adverse events (TEAEs) occurring after vaccination. Adverse events occurring before vaccination will be listed separately. Unless otherwise specified, the term "adverse events" in the following sections refers to TEAEs.

Solicited adverse events occurring 0-7 days post-vaccination, as well as solicited adverse events related to vaccination, will be categorized and analyzed by group, type of reaction (systemic and local), and the severity of each solicited adverse event as listed in Section 3.1.3.2. For these events, the number of adverse events, the number of subjects experiencing them, and the incidence rate will be calculated.

The following adverse events will be categorized and analyzed by group, System Organ Class (SOC), and Preferred Term (PT), calculating the number of events, the number of affected subjects, and the incidence rate:

- Unsolicited adverse events occurring 0-30 days after each dose;
- Adverse events occurring within 30 minutes after each dose;
- All adverse events occurring 0-30 days after each dose;
- Adverse events of special interest occurring from the first dose to 30 days after full immunization;
- Serious adverse events occurring from the first dose to 6 months after full immunization.

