8.5 Protocol Deviations

Protocol Deviations refer to any modifications or actions that do not follow the study
Study protocol/Version 1.1 /Date: Dec.8, 2023

protocol design or procedures without prior approval from the ethics committee. Actions that do not impact subject rights, safety, benefits, or the integrity, accuracy, and reliability of trial data, nor affect safety or primary endpoint evaluations, are considered protocol deviations. Actions that impact subject rights, safety, benefits, or the integrity, accuracy, and reliability of trial data, as well as those affecting safety or primary endpoint evaluations, are considered serious protocol deviations (protocol violations).

Examples of protocol deviations (including but not limited to):

- 1) Subjects did not sign the updated version of the informed consent form in a timely manner.
- 2) Storage and management of the study vaccine did not follow protocol requirements, or vaccine use was not confirmed as suitable before administration.
- 3) Diary cards and contact cards were not collected or distributed as required.
- 4) Other deviations.

Examples of protocol violations (including but not limited to):

- 1) Subjects entered the study without informed consent.
- 2) Subjects did not meet any inclusion criteria but were enrolled in the study.
- 3) Subjects met any exclusion criteria but were enrolled in the study.
- 4) Subjects did not receive the study vaccine according to the assigned vaccine allocation.
- 5) Vaccine dose, frequency, or administration route did not comply with protocol requirements.
- 6) Subjects used prohibited medications or those restricted by the protocol.
- 7) Subjects met withdrawal criteria but were not withdrawn from the study.
- 8) Other violations.

For protocol deviations/violations occurring during the study, site investigators must report the facts, process, cause, and impact of the event to the study responsible organization. The principal investigator or lead collaborative investigator should provide guidance on handling the event. Serious protocol deviations/violations must be reported to the ethics committee.

Researchers should provide targeted training for personnel involved in protocol violations to prevent recurrence and document the training process.

9. General Considerations: Regulatory, Ethical, and Trial Oversight

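### Per-dose solicited reaction rates are divided by everyone dosed, with no requirement for solicited data, and sections 7.3.3 and 8.3 disagree on who belongs to the safety population

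*Protocol*

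**What the plan says.** Section 8.3 of the protocol defines the overall set by exposure alone: "Safety Set (SS): This includes all subjects who received any dose of the vaccine". For the dose-level analyses it adds: "Safety analyses for each dose will be based on the actual number of subjects who received each dose". The first-dose and second-dose safety sets are then defined by receipt of that dose, analysed as treated. Neither definition asks for any safety data.

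Section 7.3.3 defines the safety cohort differently. Besides a dose, it lists this condition: "Have sufficient data for safety analysis (at least one dose and follow-up for safety". It also requires that no prohibited medication or vaccine was received. Section 8.3 has neither condition.

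Section 8.4.4 governs the solicited-event tables. It says that "the number of adverse events, the number of subjects experiencing them, and the incidence rate will be calculated" and names no other denominator.

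On data capture, section 5.1.9.1 has the subject record local and systemic events from the day of vaccination to day 7, and then: "On day 7 after each vaccine dose, subjects will return the Diary Card, and the researcher will review and document any adverse reactions". Section 8.5 foresees failures of this step. Among its examples of ordinary deviations is: "Diary cards and contact cards were not collected or distributed as required".

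**The concern.** Numerator and denominator rest on different conditions. To be counted as having a solicited reaction, a subject must have that reaction recorded, which in practice mostly means a returned card. To be counted in the denominator, a subject need only have been dosed. Anyone dosed but not observed for solicited events therefore pulls the rate down.

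Solicited events within 7 days of each dose are the first-listed safety endpoint (section 2.2.2), and section 3.2.1 cites the comparator's high rate of side effects. Reactogenicity by arm will be one of the trial's most-read results. The second dose is open-label (section 5.5.3.2 and synopsis), so card return could differ between arms. The disagreement between 7.3.3 and 8.3 also leaves two candidate safety populations in one document.

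**Working it through.** **Inputs from the protocol**
- Per-dose denominator: all who received the dose (8.3).
- Planned size: 150 per arm with 10% dropout (8.2). 150 × (1 − 0.10) = 135, which reproduces the stated evaluable number. That 10% concerns evaluability for the immunogenicity test, not diary return.
- Phase II vaccine-related solicited reactions, 100 µg group: 26.85% (3.2.3.2).

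**Assumptions, because the protocol gives no figure**
- m, the share of doses without a returned card: 1% to 10%.
- f, the share of those subjects' reactions recovered by another route: 0 or 0.5.
- q, the true rate among non-returners: first taken equal to the overall true rate p.
- Control-arm rate for illustration: 75%.

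**Other capture routes.** Three main routes could replace a missing card:
- On-site observation: "After each vaccine dose, the subject will be observed on-site for 30 minutes to monitor for any immediate adverse events". It covers only the first half hour.
- The Contact Card: "The Contact Card will be collected and reviewed 30 days after each dose of the vaccine". By sections 5.1.8 and 5.1.9.1 it records events from day 7 to day 30.
- Calls and questioning. Subjects are told to phone about severe symptoms (5.1.8), scheduled telephone follow-up is for SAEs and pregnancy (5.1.9.1), and staff ask about medication at each visit or contact (5.1.10). The Schedule of Activities has no separate row for a non-serious event interview.

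So f may exceed 0, but mild reactions are the likeliest to be missed.

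**Formula.** With all dosed subjects as denominator, reported rate = p − m·q·(1 − f). With q = p this is p × (1 − m(1 − f)).

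| m | p = 26.85%, f = 0 | p = 26.85%, f = 0.5 | p = 75%, f = 0 | Difference between arms, f = 0 (true 48.15 points) |
|---|---|---|---|---|
| 1% | 26.58% | 26.72% | 74.25% | 47.7 |
| 2% | 26.31% | 26.58% | 73.50% | 47.2 |
| 5% | 25.51% | 26.18% | 71.25% | 45.7 |
| 10% | 24.17% | 25.51% | 67.50% | 43.3 |

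The relative loss is the same at every p, so the absolute loss grows with p. At 10% missing it is 2.7 points at 26.85% and 7.5 points at 75%.

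**Unequal loss (f = 0).** With 2% missing on LZ901 and 10% on control, the difference is 67.50 − 26.31 = 41.2 points. With the two shares reversed it is 73.50 − 24.17 = 49.3 points. The contrast can move either way.

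**Informative loss.** Take p = 80% and m = 5%, both assumed, with f = 0. The all-dosed rate is 75% if every non-returner reacted (q = 1) and 80% if none did (q = 0). A returned-card denominator gives (80 − 5)/95 = 78.9% and 80/95 = 84.2% respectively. It is exact when q = p and not otherwise.

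**The case against.** The strongest reply is that the protocol nowhere says how a subject without a card is counted. Missing-diary rules and table denominators usually belong in the SAP, which is not shown. Section 7.3.3 asks for sufficient data and points to section 5.1.9, where follow-up includes the card, and the analysis sets are settled at a blinded review before lock. A missing card is also not always missing data: there are later visits, and the section 8.5 example covers late collection as well. Safety is descriptive, with no hypothesis attached.

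Much of this stands as a limit on size and wording. A reader might infer that the protocol contains a rule scoring non-returners as reaction-free. It does not; that result is only the arithmetic consequence when nothing is recorded for them. Nor does classing uncollected cards as ordinary deviations keep those subjects in, because the Safety Set has no deviation-based exclusion at all.

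The reply does not remove the point. Section 8.3 states a denominator and does not leave it open, so a SAP using another would depart from the protocol. The condition in 7.3.3 is neither per dose nor specific to solicited data. Whether the 30-minute observation alone satisfies it is unclear, and it conflicts with 8.3 in any case.

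**Conclusion.** The point holds as a modest, cheaply corrected weakness. The stated denominator understates solicited incidence whenever some non-returners had reactions that were not otherwise recorded. Under the assumed 1–10% loss, unrelated to reaction and with no recovery, 26.85% would be reported as 26.6% to 24.2%. Recovering half of the missed events halves the drop. At 1–2% loss the effect is about half a point or less at that rate.

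Three stronger readings are tempting but unsupported:
- The 10% dropout in section 8.2 might be read as a ceiling on diary loss. It was set for immunogenicity evaluability and bounds nothing here.
- The Phase II 26.85% might be set against the 100% for the active control in Phase I (3.2.3.1) to give a gap of about 73 points. One is vaccine-related solicited reactions and the other is any adverse event, in different trials.
- The understatement might be taken to favour LZ901. With equal loss the gap narrows, which works against its tolerability advantage. With unequal loss the direction depends on which arm loses more cards.

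**What to change.** 1. Reconcile sections 7.3.3 and 8.3 so that the protocol has one definition of the safety population.
2. In sections 8.3 and 8.4.4, add a per-dose denominator for solicited events: subjects who received the dose and have a returned Diary Card, or another documented solicited-event assessment made after the 30-minute observation and covering days 0–7. The last condition is needed because the on-site observation falls on day 0 and would otherwise readmit every dosed subject.
3. Keep all dosed subjects as the denominator for 30-minute events, unsolicited events, AESIs and SAEs.
4. Report the number without solicited data by arm and dose, and show the all-dosed rate as a sensitivity display.

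The cost is a few sentences, one extra denominator column and slightly smaller denominators. The change discloses informative diary loss but does not cure it. Reporting the missing counts lets a reader judge how much that matters.

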5.4.6 Reserve vaccine

Sixty reserve vaccine doses will be prepared, with 30 doses each of the experimental vaccine and the active control vaccine. If a study vaccine is found to be damaged during the study, the investigator can obtain the reserve vaccine number for the corresponding group through the randomization system and administer the reserve vaccine labeled with the appropriate vaccine number. (The investigator only sees the randomization number; the true group assignments for the study and reserve vaccines are pre-loaded into the system and remain blinded throughout the study. Additional reserve doses may be added if the existing stock is insufficient.)

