5.5.3.2 Unblinding Procedures

In this study, unblinding is required before the administration of the second dose, as the dosing intervals differ between the experimental group (30 days) and the control group (60 days). The unblinding process must be initiated by the principal investigator, who submits an unblinding request to the sponsor, and a record of the unblinding must be maintained.

In the event of group adverse events or study interruption for any reason, early unblinding may be conducted with the mutual agreement of the sponsor and the research team.

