10.1.5 Biological Sample Management

Subject blood samples used for immunogenicity testing are to be managed by designated personnel, with established protocols for sample storage and temperature monitoring. On weekdays, storage temperatures must be monitored and recorded daily. On holidays, monitoring and recording may be arranged according to site-specific conditions, provided automatic temperature monitoring and alarm systems are in place.

Whole blood samples should be transported to the testing laboratory or sample processing laboratory at 2-8°C. Processed cellular samples must be stored and transported under low-temperature conditions (liquid nitrogen) to the testing laboratory. Serum samples should be transported to the testing laboratory under frozen conditions (using dry ice, low-temperature ice packs, or other freezing methods). Backup samples should not be transported simultaneously with test samples and must be stored by the investigator at $\leq -20^{\circ}\text{C}$ until the clinical report is completed and processed as confirmed by the sponsor.

Blood samples should be transported to the testing center in batches according to the relevant SOPs.

Proper handover management must be maintained throughout the process, with the investigator, sample transporter, and laboratory personnel keeping accurate records.

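### Protocol 8.3 relies on a blinded meeting to settle the per-protocol set, but the investigator and sponsor at that meeting already know the allocation from the dose-2 unblinding

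*Protocol*

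**What the plan says.** - **Who settles the sets (8.3):** "The determination of the above analysis sets will occur in a blinded data review meeting before database lock". Four parties are named as contributing: statisticians, data managers, the sponsor and the principal investigator.
- **What the PPS requires (8.3):** eligibility, randomization, completed vaccination, and baseline and day-30 results. Subjects are then removed for deviations considered major and considered to affect the immunogenicity evaluation.
- **What the PPS is used for (8.4.2):** it is the main set for the cellular endpoint. Non-inferiority is concluded when the lower 95% Miettinen-Nurminen limit exceeds -10%.
- **Unblinding (5.5.3.2):** "In this study, unblinding is required before the administration of the second dose, as the dosing intervals differ". The principal investigator starts the process and is the one "who submits an unblinding request to the sponsor".
- **Design (synopsis, overall design):** double-blind before dose 2, open-label at dose 2.
- **Dates (5.1.7 and Schedule of Activities):** dose 2 falls at D30 in the experimental arm and D60 in the control arm. The second bleed falls at D60 and D90 respectively.
- **The same meeting in 10.2.11:** the populations are defined there before lock, and blinding is not mentioned.
- **Reserve vaccine (5.4.6):** the true assignments of study and reserve vaccine held in the system are said to "remain blinded throughout the study".

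**The concern.** A blinded data review protects a per-protocol analysis because those who decide exclusions cannot favour an arm. Here two of the four parties named for the meeting are the two through whom the dose-2 unblinding runs. Every PPS subject has completed vaccination, so every one of them has passed through that unblinding before the meeting. Statisticians and data managers who were never told the allocation could still read it from a listing that shows when dose 2 or the second bleed took place.

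This matters because the decision is partly discretionary and feeds the primary comparison directly. Section 8.5 sorts departures into deviations and violations, gives open-ended examples of each, and does not define the term major that 8.3 uses. The protocol also does not say that ELISA and flow-cytometry results are held back until the sets are final.

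**Working it through.** **1. The texts side by side**

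| Question | 8.3 | 5.5.3.2, synopsis, schedule |
|---|---|---|
| Is allocation known when the sets are decided? | No (blinded meeting) | Yes for investigator and sponsor: unblinding precedes dose 2, and dose 2 precedes the day-30 sample and database lock |
| Can others at the meeting infer the arm? | Not addressed | Yes, if listings show dose 2 (D30 or D60) or the second bleed (D60 or D90) |
| Are cell results withheld? | Not stated | Not stated in 10.2.11 either |

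**2. The plan's own figure**

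Inputs from 8.2: CD4+ 85% vs 75%, CD8+ 55% vs 45%, 135 evaluable per arm (150 × 0.90), one-sided 0.025. The margin of 10 points is in 8.1.

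Power = Φ[(pT − pC + 0.10)/SE − 1.96], with SE = √[pT(1 − pT)/135 + pC(1 − pC)/135].

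- CD4+: SE = 0.0483, power 98.5%.
- CD8+: SE = 0.0606, power 91.0%.
- Both together, if independent: 0.985 × 0.910 = 89.7%.

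The stated power of about 90% reproduces. The sample size is not in question.

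**3. Effect of one-sided exclusions on the experimental rate**

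Assumption: all k excluded subjects are experimental-arm non-responders. The new rate is p × 135/(135 − k).

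| | k = 5 | k = 8 |
|---|---|---|
| CD8+, p = 55% | 0.55 × 135/130 = 57.1% (+2.1) | 0.55 × 135/127 = 58.5% (+3.5) |
| CD4+, p = 85% | 0.85 × 135/130 = 88.3% (+3.3) | 0.85 × 135/127 = 90.4% (+5.4) |

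**4. How few exclusions move the decision near the margin**

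Miettinen-Nurminen lower limits, with illustrative control counts close to the planned 75% and 45% of 135:

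| Endpoint | Experimental | Control | Lower limit | Non-inferior? |
|---|---|---|---|---|
| CD4+ | 101/135 | 101/135 | −10.4% | no |
| CD4+, 1 non-responder removed | 101/134 | 101/135 | −9.8% | yes |
| CD8+ | 63/135 | 61/135 | −10.4% | no |
| CD8+, 2 non-responders removed | 63/133 | 61/135 | −9.7% | yes |

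**5. Effect on the error rate at the margin**

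The true difference is set at −10 points. The type I error is approximately Φ(bias/SE − 1.96).

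- CD4+ (65% vs 75%, SE 0.0554): removing 4 experimental non-responders adds 1.98 points and gives about 0.055. Removing 8 adds 4.09 points and gives about 0.11.
- CD8+ (35% vs 45%, SE 0.0593): removing 4 adds 1.07 points and gives about 0.038. Removing 8 adds 2.20 points and gives about 0.056.

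The nominal level is 0.025.

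**The case against.** Several points on the other side stand.

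- Most PPS conditions are objective and already written down: eligibility, completed vaccination, both samples, dose and visit windows, and a list of violations in 8.5. Judgement is confined mainly to which deviations are major and affect immunogenicity.
- Section 5.5.3.2 does not say that statisticians or data managers receive the allocation. A reader might infer that everyone at the meeting is formally unblinded. The text supports that only for the investigator and sponsor; for the others the route is the dates.
- Picking out non-responders deliberately needs the cell results as well as the arm. The protocol does not say that the meeting has them, only fails to say that it does not. The arithmetic therefore shows sensitivity and does not predict what will happen.
- Section 5.4.6 concerns assignments held in the randomization system for damaged and reserve vaccine. It sits awkwardly with the open-label second dose, but it is not about the PPS.

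A reader might also infer that the flow-cytometry reading is unblinded and that assay run is confounded with arm, since "Each biological sample should correspond to the subject study ID" and "Blood samples should be transported to the testing center in batches according to the relevant SOPs" while the second bleeds fall about a month apart. The documents do not support that. Sections 7.6.3, 7.6.4 and 10.1.5 leave numbering, assay procedure and shipment to SOPs or a laboratory manual not shown. Study numbers are sequential, so they do not themselves disclose the arm. Section 10.1.5 describes transport batches, not assay runs, and cells are frozen in liquid nitrogen, so pooled reading is possible. Laboratory blinding is unstated, not shown to be absent.

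**Conclusion.** The contradiction between 8.3 and 5.5.3.2 with the synopsis is certain from the text. The blinding claimed for deciding the primary analysis set does not exist with respect to arm for the investigator and sponsor, and visit dates undo it for anyone reading ordinary listings. An unseen analysis plan could add detail but would not remove the conflict in the protocol.

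The possible effect is 2.1 to 5.4 points on the experimental rate for 5 to 8 exclusions, with one or two enough to change the conclusion close to the margin. Those sizes rest on assumptions: 135 evaluable per arm, the planned experimental rates, and every excluded subject being an experimental non-responder. They are an upper illustration and do not suggest that anyone would act this way. The change should be made. It does not affect sample size, power or trial conduct.

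**What to change.** Replace the closing sentence of 8.3 with text to this effect:

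1. The PPS exclusion rules, including a closed list of major deviations and the visit and dose windows already in the protocol, are fixed before the first dose-2 unblinding and applied by program.
2. Dose-2 timing is checked by program against the subject's assigned schedule and passed on only as an in-window or out-of-window flag. Listings that gave only days since dose 2 could not settle this question.
3. Residual cases are decided by staff without access to allocation, on listings stripped of arm-revealing dates, before ELISA and flow-cytometry results are released or merged.
4. The meeting is called blinded only in that stated sense: blind to immunogenicity results.

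Bring 10.2.11 into line, and limit the statement in 5.4.6 to the period before dose-2 unblinding. As a suggestion only, confirm in the laboratory SOP that readers are blind to arm and that runs are balanced by arm.

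The cost is somewhat earlier planning and programming. Dosing, visits and sample size are unchanged.
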